2.7.1.2 Requirements of ClinicalTrials.gov and EudraCT

For the legal requirements of ClinicalTrials.gov and EudraCT, two required tables on treatment emergent AEs: non-serious AEs with an incidence greater than 3%, and deaths and serious AEs (SAEs) including the events suspected to be related to study treatment, will be provided by SOC and PT on the Safety Set. The cut-off of 3% can be re-evaluated based on number of participants.

If for a same participant, several consecutive AEs (irrespective of study treatment causality, seriousness and severity) occurred with the same SOC and PT:

- a single occurrence will be counted if there is ≤ 1 day gap between the end date of the preceding AE and the start date of the consecutive AE

- more than one occurrence will be counted if there is > 1 day gap between the end date of the preceding AE and the start date of the consecutive AE

For occurrence, the presence of at least one SAE / SAE suspected to be related to study treatment / non SAE has to be checked in a block e.g., among AE's in a ≤ 1 day gap block, if at least one SAE is occurring, then one occurrence is calculated for that SAE.

The number of deaths resulting from SAEs suspected to be related to study treatment and SAEs irrespective of study treatment relationship will be provided by SOC and PT.

These tables will be provided at the final analysis after completion of the study.

2.7.2 Deaths

A separate summary for death including on treatment and post treatment deaths will be provided. If there are few deaths, only listing will be provided.

2.7.3 Laboratory data

All laboratory data will be listed by treatment group, participant, and visit and if normal ranges are available abnormalities will be flagged.

For Hematology and Serum chemistry, central laboratory data will be included in the summary tables. Local laboratory data will be listed and be included in the notable summary tables, but will not be included in the by-visit summary tables.

For Urinalysis, handling of data will depend on country (China, non-China) as follows:

- Non-China participants

For those who have only local laboratory data, local data will be included in the summary tables;

For those who have both of local and central laboratory data, local data will be included in the summary tables;

For those who have only central laboratory data, central data will be included in the summary tables.

Both of local and central data can be listed.

- China participants

For those who have only central laboratory data, central data will be included in the summary tables;

For those who have both of local and central laboratory data, central data will be included in the summary tables;

For those who have only local laboratory data, local data will be included in the summary tables.

Both of local and central data can be listed.

For by-visit summary tables, scheduled visits (including remapped visits following the assessment window in [Section 2.1.1.5](#)) will be considered in the analysis. Unscheduled visits will not be included.

For notable summary tables, all post-baseline visits including unscheduled visits will be considered in the analysis.

[Table 2-14](#) presents overview of safety analysis on laboratory data.

Table 2-14 Overview of safety analyses on laboratory data

Analysis	Period	Treatment groups	Summary by visit	Notables
Primary analysis	Double blind	
• LOU064 25mg• Placebo	X (up to Week 24)	X (up to Week 24 including unscheduled visits of Week 24)
	Entire study	
• LOU064 25mg• Placebo• Transitioned to LOU064 25mg (under LOU064 treatment)	X (after Week 24)	X
Final analysis	Entire study	
• LOU064 25mg• Placebo• Transitioned to LOU064 25mg (under LOU064 treatment)	X	X

X: to be provided

The summary of laboratory evaluations will be presented for three groups of laboratory tests (Hematology, Serum chemistry and Urinalysis).

For continuous variables, descriptive summary statistics for the change from baseline to each study visit will be presented. These descriptive summaries will be presented by study period, laboratory test and treatment group. Change from baseline will only be summarized for participants with both baseline and post baseline values and will be calculated as:

$$\text{change from baseline} = \text{post baseline value} - \text{baseline value}$$

For categorical variables, descriptive statistics will be presented in contingency tables including the number and percentage of participants for each category.

For Hematology and Serum chemistry, the maximum change from baseline (maximum decrease and maximum increase) will be summarized by treatment group during the double-blind period.

In addition, for laboratory parameters where normal ranges are available, shift tables will be provided for all parameters to compare a subject's baseline laboratory evaluation relative to the worst on-treatment value. For the shift tables, the normal laboratory ranges will be used to evaluate whether a particular laboratory test value was normal, low, or high for each visit value relative to whether or not the baseline value was normal, low, or high. These summaries will be presented by study period, laboratory test and treatment group.

Box plots for selected parameters will be provided by treatment group and study period.

The following laboratory parameters will be analyzed with respect to numerical Common Terminology Criteria for Adverse Event (CTCAE) grades (version 5.0), given in [Table 2-15](#): hemoglobin, platelets, white blood cell count, neutrophils, lymphocytes, creatinine, creatinine kinase, total bilirubin (TBL), gamma-glutamyl transferase (GGT), alanine aminotransferase (ALT), aspartate aminotransferase (AST), alkaline phosphatase (ALP), total cholesterol, triglycerides, amylase, and lipase.

CTCAE grades based on lab results alone will be applied programmatically. Clinical assessments (in *italic* below) will not be considered. In case of missing baseline laboratory assessment, it will be assumed as normal. The number and percentage of participants with CTCAE grade newly occurring or worsening after baseline will be presented. A case is considered as newly occurring abnormality if the value is not notable or missing at baseline but is notable thereafter. A case is considered as worsening abnormality if the value is notable at baseline and at least one post-baseline value is worse than baseline.

Shift tables will be provided on CTCAE grades to compare baseline relative to the worst grade. These summaries will be split into hematology and chemistry and will be presented by study period and treatment group.

Table 2-15 CTCAE grades for laboratory parameters to be analyzed

CTCAE term	Laboratory assessment	Grade 1	Grade 2	Grade 3	Grade 4
Anemia	Hemoglobin (Hgb)	<LLN-10.0 g/dL	<10.0-8.0 g/dL	<8.0 g/dL	Life-threatening consequences
Platelet count decreased	Platelet	<LLN-75,000/mm	<75,000-50,000/mm ³	<50,000-25,000/mm ³	<25,000/mm ³
White blood cell decreased	White blood cell	<LLN-3000/mm ³	<3000-2000/mm ³	<2000-1000/mm ³	<1000/mm ³
Neutrophil count decreased	Neutrophils	<2000-1500/mm ³	<1500-1000/mm ³	<1000-500/mm ³	<500/mm ³
Lymphocyte count decreased	Lymphocytes	<1500-800/mm ³	<800-500/mm ³	<500-200/mm ³	<200/mm ³
INR increased	INR	>1.2 - 1.5	>1.5 - 2.5	>2.5	-
Creatinine increased	Serum creatinine	>ULN-1.5 x ULN	>1.5 - 3.0 x ULN	>3.0 - 6.0 x ULN	>6.0 x ULN
Creatinine kinase increased	Serum creatinine kinase	>ULN-2.5 x ULN	>2.5 - 5.0 x ULN	>5.0 - 10.0 x ULN	>10.0 x ULN
Blood bilirubin increased	Total bilirubin (TBL)	>ULN - 1.5 x ULN	>1.5 - 3.0 x ULN	>3.0 - 10.0 x ULN	>10.0 x ULN
GGT increased	Gamma-glutamyl transferase (GGT)	>ULN - 2.5 x ULN	>2.5 - 5.0 x ULN	>5.0 - 20.0 x ULN	>20.0 x ULN

Alanine aminotransferase increased	Alanine aminotransferase (ALT)	>ULN - 3.0 x ULN	>3.0 - 5.0 x ULN	>5.0 - 20.0 x ULN	>20.0 x ULN
Aspartate aminotransferase increased	Aspartate aminotransferase (AST)	>ULN - 3.0 x ULN	>3.0 - 5.0 x ULN	>5.0 - 20.0 x ULN	>20.0 x ULN
Alkaline phosphatase increased	Alkaline phosphatase (ALP)	>ULN - 2.5 x ULN	>2.5 - 5.0 x ULN	>5.0 - 20.0 x ULN	>20.0 x ULN
Total cholesterol increased	Total Cholesterol	>ULN – 7.75 mmol/L	>7.75 – 10.34 mmol/L	>10.34 – 12.92 mmol/L	>12.92 mmol/L
Triglyceride increased	Triglyceride	>=1.71 – 3.42 mmol/L	>3.42 – 5.7 mmol/L	>5.7 – 11.4 mmol/L	>11.4 mmol/L
Amylase increased	Amylase	>ULN – 1.5 x ULN	>1.5 – 2.0 x ULN	>2.0 – 5.0 x ULN	>5.0 x ULN
Lipase increased	Lipase	>ULN – 1.5 x ULN	>1.5 – 2.0 x ULN	>2.0 – 5.0 x ULN	>5.0 x ULN

ULN: Upper limit of normal range; LLN: Lower limit of normal range.

To evaluate potential drug-induced liver injury, newly occurring liver enzyme abnormalities will also be summarized based on the event criteria given in [Table 2-16](#). For the combination criteria of parameters, except potential Hy's Law case, all the elevations must occur at the same post-baseline timepoint. A case will be considered as newly occurring if a criterion is not met or missing at baseline but is met thereafter. A case is considered as worsening abnormality if the value is notable at baseline and at least one post-baseline value during is worse than baseline.

Similarly, participants meeting specific renal alert criteria at any post-baseline will be summarized according to [Table 2-17](#).

In addition, for liver enzyme test abnormalities,

For participants meeting the criteria [ALT or AST >5x ULN] or [ALT or AST>3xULN & TBL >2xULN & ALP <2xULN], graphical case (per participant) representation to include graph of liver enzymes over time (ALT, AST, TBL, ALP, based on xULN) with treatment exposure and concomitant medications.

Table 2-16 Liver enzyme abnormalities

Parameter	Criterion
ALT	>3xULN; >5xULN; >8xULN; >10xULN; >20xULN
ALT or AST	>3xULN; >5xULN; >8xULN; >10xULN; >20xULN
(ALT or AST) & TBL	>3xULN & (TBL>1.5xULN; >2xULN)
(ALT or AST) & INR	>3xULN & INR>1.5
TBL	>1xULN; >1.5xULN; >2xULN;
ALP	>1.5xULN; >2xULN; >5xULN
ALP & TBL	>3xULN; >5xULN & TBL>2xULN
(ALT or AST) & TBL & ALP	ALT or AST>3xULN & TBL >2xULN & ALP <2xULN (Potential Hy's Law)

Table 2-17 Specific renal alert criteria

Parameter	Notable criterion
Serum creatinine	increase 25% – <50% (%change from baseline), increase \geq 50%
Dipstick proteinuria	\geq 3+ (Newly occurring)
Dipstick hematuria (occult blood)	\geq 3+ (Newly occurring)

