Demography	X														
Pregnancy and assessments of fertility ²	XS	S		S	S	S	S	S	S	S	S	S	S	S	S
Evidence of urticaria	S	S													
Hepatitis screen	X														
Relevant medical history	X														
Dispense participants' eDiary ³	S											S	S		
CSU History and prior urticaria treatment	X														
Cardiovascular history	X														

Period	Screening	Treatment											Follow-up	Unscheduled visit	
Visit Name	Screening	Baseline/ Randomization ¹	week 2 ¹	week 4	week 8	week 12 ¹	week 16	week 20	week 24	week 32	week 40	Early treatment discontinuation	week 52/Study discontinuation ¹	week 56/Safety FU/Study completion	Unscheduled visit
Days	-28 to -1	1	15	29	57	85	113	141	169	225	281		365	394	-
Physical Examination ⁴	S	S	S	S	S	S	S	S	S	S	S	S	S	S	S
Height and Weight ⁵	X	X				X			X			X	X	X	X
Vital Signs	X	X	X	X	X	X	X	X	X	X	X	X	X	X	X
Electrocardiogram (ECG)	X	X	X ⁶			X ⁶			X			X	X ⁶	X	X
Subject's eDiary review ⁷		S	S	S	S	S	S	S	S	S	S	S	S		S
DLQI ⁸		X		X		X			X			X	X		X
Study drug dispensation		X		X	X	X	X	X	X	X	X				
Background medication dispensation and compliance assessment ¹⁶	X	X		X	X	X	X	X	X	X	X	X	X	X	
Rescue medication dispensation and usage ¹⁰	X	X		X	X	X	X	X	X	X	X	X	X		

Period	Screening	Treatment											Follow-up	Unscheduled visit	
Visit Name	Screening	Baseline/ Randomization ¹	week 2 ¹	week 4	week 8	week 12 ¹	week 16	week 20	week 24	week 32	week 40	Early treatment discontinuation	week 52/Study discontinuation ¹	week 56/Safety FU/Study completion	Unscheduled visit
Days	-28 to -1	1	15	29	57	85	113	141	169	225	281		365	394	-
Clinical Chemistry	X	X	X	X	X	X	X	X	X	X	X	X	X	X	X
Hematology	X	X	X	X	X	X	X	X	X	X	X	X	X	X	X
Urinalysis	X	X	X	X	X	X	X	X	X	X	X	X	X	X	X
Coagulation Panel	X	X		X		X			X		X	X	X	X	X
Hepatitis B re-activation monitoring ¹⁴				X	X	X	X	X	X	X	X	X	X	X	X
Eligibility assessment for extension study ¹⁷													X		

Period	Screening	Treatment											Follow-up	Unscheduled visit	
Visit Name	Screening	Baseline/ Randomization ¹	week 2 ¹	week 4	week 8	week 12 ¹	week 16	week 20	week 24	week 32	week 40	Early treatment discontinuation	week 52/Study discontinuation ¹	week 56/Safety FU/Study completion	Unscheduled visit
Days	-28 to -1	1	15	29	57	85	113	141	169	225	281		365	394	-
Prior and concomitant medication												X			
Adverse Events												X			
Study completion information												X			

¹ Participant to come fasting for ≥8 h (ideally overnight) to visits: Baseline/Randomization, week 2, week 12 and week 52

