8.4.1 Laboratory evaluations

A central laboratory will be used for analysis of all specimens detailed in this section ([Table 8-9](#)) unless noted otherwise. Details on the collections, shipment of samples and reporting of results by the central laboratory are provided to investigators in the laboratory manual.

[figure not shown]
If participants cannot visit the site for protocol specified safety lab assessments (per [Section 4.6](#)), an alternative lab (local) collection may be used.

Clinically notable laboratory findings are defined in [Section 16.1](#).

Clinically significant abnormalities must be recorded on the relevant section of the eCRF capturing medical history/current medical conditions/AEs.

Table 8-9 Laboratory assessments

Test Category	Test Name
Hematology	Hematocrit, Hemoglobin, [in the case of clinically significant anemia the following parameters will be assessed: Ery. Mean Corpuscular Hemoglobin (MCH), Ery. Mean Corpuscular Hemoglobin Concentration (MCHC), Ery. Mean Corpuscular Volume (MCV)], Platelets, Erythrocytes, Leukocytes, and Differential (Basophils, Eosinophils, Lymphocytes, Monocytes, Neutrophils, Bands)
Chemistry	Albumin, Alkaline phosphatase (ALP), Alanine Aminotransferase (ALT), Aspartate Aminotransferase (AST), Gamma-glutamyl transferase (GGT), Lactate dehydrogenase (LDH), Calcium, Magnesium, Phosphate, Chloride, Sodium, Potassium, Creatinine, Creatine Kinase (CK), Direct Bilirubin, Indirect Bilirubin (in case of clinically significant elevation), Total Bilirubin, Total Cholesterol, Low Density Lipoprotein (LDL) Cholesterol, High-Density Lipoprotein (HDL) Cholesterol, Total Protein, Triglycerides, Urea Nitrogen or Urea, Uric Acid, Amylase, Lipase. C-reactive protein (CRP), estimated Glomerular Filtration Rate (eGFR): in all patients at screening, baseline, weeks 12, 24 and 52 and when deemed necessary by the investigator at later visits.

Test Category	Test Name
	Fasting glucose assessed at randomization, weeks 2, 12 and 52.
Urinalysis	Done on site (unless prohibited by local guidelines, then sample to be sent to central laboratory) Macroscopic Panel (Dipstick) (Color, Bilirubin, Occult Blood, Macroscopic Blood, Glucose, Ketones, Leukocytes esterase, Nitrite, pH, Protein, Specific Gravity, Urobilinogen)
Coagulation	Prothrombin time (PT), International normalized ratio (INR), Activated partial thromboplastin time (APTT)

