X: to be recorded, BSL: baseline, ETD: early treatment discontinuation, SD: study discontinuation

¹ only post-baseline assessments² pre and post dose

* C-reactive protein (CRP), estimated Glomerular Filtration Rate (eGFR): assessed at screening, baseline, weeks 12, 24 and 52. Fasting glucose assessed at baseline, weeks 2, 12 and 52.

Table 2-7 shows the assessment windows for the assessments collected at every visit (i.e., Vital signs, Clinical Chemistry, Hematology, Urinalysis).

If more than one assessment fall into the interval,

- Then if there is the scheduled visit recorded in eDiary or eCRF, this visit will be chosen.
- If no, the earliest visit day will be chosen.

For example, when a participant discontinued study treatment after completing Week 2 and Week 4, and ETD visit occurred on Day 35 and SD visit occurred on Day 80, the ETD visit will be mapped to Week 8 and SD visit will be remapped to Week 12.

If a participant visited the site earlier than scheduled visit day, e.g., Week 4 on Day 25, ETD visit on Day 29, ETD visit will be remapped to Week 4. As the participant already performed Week 4 scheduled visit, the remapped Week 4 (ETD visit) will not be used.

If a participant visited the site late than scheduled visit day, e.g., Week 4 on Day 25, ETD visit on Day 58, SD visit on Day 85, both ETD visit and SD visit will be remapped to Week 12. In this case, ETD visit will be used as Week 12, and Week 8 will be missing.

Table 2-7 Assessment window for vital signs, clinical chemistry, hematology, urinalysis until Week 52

Assessment visit	Scheduled Visit Day	Assessment Window
Week 2	15	Day 2 to Day 15
Week 4	29	Day 16 to Day 29
Week 8	57	Day 30 to Day 57
Week 12	85	Day 58 to Day 85
Week 16	113	Day 86 to Day 113
Week 20	141	Day 114 to Day 141
Week 24	169	Day 142 to Day 169
Week 32	225	Day 170 to Day 225
Week 40	281	Day 226 to Day 281
Week 52	365	Day 282 to Day 365

For the assessments which are not collected at every visit (e.g., DLQI), assessment window will be combined. For example, DLQI is collected at Week 4, Week 12, Week 24 and Week 52. The assessment window will be combined as follows:

Table 2-8 Assessment window for DLQI until Week 52

Assessment visit	Scheduled Visit Day	Assessment Window
Week 4	29	Day 2 to Day 29
Week 12	85	Day 30 to Day 85
Week 24	169	Day 86 to Day 169
Week 52	365	Day 170 to Day 365

Table 2-9 shows the assessment windows of days for each assessment.

Table 2-9 Assessment windows by assessment

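### SAP 2.7.3 sets a normally fasting triglyceride baseline against the worst of all post-baseline values, most of them from visits with no fasting instruction

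*SAP*

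**What the plan says.** **Fasting.** Footnote 1 of Protocol Table 8-1 reads: "Participant to come fasting for ≥8 h (ideally overnight) to visits: Baseline/Randomization, week 2, week 12 and week 52". No other visit has such an instruction.

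**Sampling.** Triglycerides are in the chemistry panel of Protocol Table 8-9 ("Total Protein, Triglycerides, Urea Nitrogen or Urea, Uric Acid, Amylase, Lipase") with no visit or fasting restriction. SAP 2.1.1.5 lists chemistry among "the assessments collected at every visit (i.e., Vital signs, Clinical Chemistry, Hematology, Urinalysis". Both documents tie glucose to the fasting visits: the protocol has "Fasting glucose assessed at randomization, weeks 2, 12 and 52" and the SAP has "Fasting glucose assessed at baseline, weeks 2, 12 and 52". Neither does so for triglycerides.

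**Baseline.** Under SAP 2.1.1.2 the safety baseline is the last assessment on or before the day of first dose. That is normally the fasting Day 1 sample.

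**Grading.** SAP Table 2-15 grades triglycerides at absolute cut-offs (Grade 1 from 1.71 mmol/L, then above 3.42, 5.7 and 11.4) with no fasting condition. SAP 2.7.3 says of the graded parameters: "The number and percentage of participants with CTCAE grade newly occurring or worsening after baseline will be presented". One post-baseline value worse than baseline is enough to count, the CTCAE shift runs to the worst grade, and "For notable summary tables, all post-baseline visits including unscheduled visits will be considered in the analysis". For haematology and chemistry, "the maximum change from baseline (maximum decrease and maximum increase) will be summarized by treatment group during the double-blind period". No rule flags or separates triglyceride samples taken without fasting.

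**The concern.** Triglycerides can rise after a meal. If baseline is fasting and most later samples need not be, a participant can pass from normal to Grade 1 because of breakfast. A worst-value rule needs only one such sample. The percentage with a new or worse grade is then higher than it would be under like-for-like sampling.

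The stake is how the absolute percentages are read. In the double-blind period a placebo column shows the background rate. After Week 24 every participant still on treatment takes open-label remibrutinib. Readers of the entire-study tables must then take the percentage at face value, and it mixes meal status with any drug effect. The sponsor allowed for fasting with glucose, which Table 2-15 does not grade, but not with triglycerides, which it does.

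**Working it through.** The documents state no figure on this point, so there is none to reproduce. The visit counts below come from the documents. The simulation does not.

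**1. Visit count (Protocol Table 8-1).**
- Scheduled post-baseline chemistry visits to Week 24: Weeks 2, 4, 8, 12, 16, 20, 24 = 7. Fasting: Weeks 2 and 12. Without instruction: 7 - 2 = 5 (71%).
- To Week 52, add Weeks 32, 40 and 52 = 10. Fasting: Weeks 2, 12 and 52. Without instruction: 10 - 3 = 7 (70%).
- Early treatment discontinuation and unscheduled samples also carry no instruction.
- Week 56 does not normally enter. With a last dose at Day 365, the on-treatment period ends at 365 + 28 = Day 393, and Week 56 is Day 394.

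**2. Illustrative size.** Assumptions, none of them in the documents: log-normal triglycerides, fasting median 1.1 or 1.3 mmol/L, between-person log SD 0.45, within-person log SD 0.15 or 0.25, no drug effect, fasting baseline, and a constant addition at all five visits without a fasting instruction. A participant is flagged if the worst post-baseline grade (Table 2-15 cut-offs) exceeds the baseline grade.

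| Median / within-person SD | 2 fasting visits | 7 visits, no meal effect | 7 visits, +0.1 | 7 visits, +0.3 | 7 visits, +0.5 |
|---|---|---|---|---|---|
| 1.1 / 0.15 | 8.0% | 14.9% | 18.4% | 28.6% | 42.7% |
| 1.1 / 0.25 | 13.8% | 26.7% | 30.4% | 40.1% | 52.4% |
| 1.3 / 0.15 | 10.9% | 19.8% | 23.9% | 35.1% | 48.9% |
| 1.3 / 0.25 | 18.2% | 33.7% | 37.7% | 47.4% | 58.8% |

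**3. Share of flags due to meals** = (rate with addition - rate without) / rate with addition. At +0.3 the extremes are (28.6 - 14.9) / 28.6 = 48% and (47.4 - 33.7) / 47.4 = 29%. At +0.1 they are (18.4 - 14.9) / 18.4 = 19% and (37.7 - 33.7) / 37.7 = 11%. At +0.5 they are (42.7 - 14.9) / 42.7 = 65% and (58.8 - 33.7) / 58.8 = 43%. With a multiplier of 1.1 to 1.5 in place of an addition, medians up to 1.5 and within-person SD up to 0.30, the share runs from 14% to 72%.

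**4. What is not meals.** The step from two fasting visits to seven visits with no meal effect (8.0-18.2% to 14.9-33.7%) comes only from taking the worst of more values.

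**5. Between-arm contrast.** With an assumed 10% drug effect on the fasting component and a constant addition of 0.1 to 0.5, the risk difference is about 9-11 points on all seven visits and about 6-8 on the two fasting visits. With widely varying additions (exponential, mean 0.3 or more), the test statistic mostly favours the fasting visits instead.

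**The case against.** The strongest reply is that inclusive worst-value screening is a legitimate, cautious choice for safety. Both double-blind arms follow one schedule, with a placebo column beside remibrutinib. The by-visit change-from-baseline summaries at Weeks 2, 12 and 52 already give a largely fasting comparison, and every value is listed. Lipids are not among the potential risks in Protocol 4.5 or the selected adverse events of special interest in SAP 2.7.1.1. All of this stands, and it limits the weight of the point. It does not make the graded percentages interpretable, because the by-visit summaries give neither CTCAE incidence nor shifts.

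Three stronger readings are tempting, and the documents support none of them:

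- A reader might infer that the new or worse grades largely reflect meals. The documents give no meal effect and do not say that participants eat before the other visits, only that fasting is not asked for. At +0.3 mmol/L meals account for under half of the flags. The rest come from taking the worst of seven values.
- A reader might infer that meal noise buries a drug effect in the double-blind comparison. Under a constant addition the risk difference is not smaller on all visits. The claim depends on how variable meal effects are, which the documents do not address.
- A reader might infer that every baseline is fasting. A missing Day 1 value falls back to screening, which has no fasting instruction, and a wholly missing baseline is treated as normal.

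**Conclusion.** The mismatch is in the text of the plan: a normally fasting baseline, a worst-value rule over all visits, a fasting instruction at only 2 of 7 double-blind visits (3 of 10 to Week 52), and no fasting rule for triglycerides. Absolute incidence, shift to worst grade and double-blind maximum increase are inflated to the extent that participants eat before the other visits. On the assumed inputs with +0.3 mmol/L, the inflation is about 13 to 15 percentage points (40.1 - 26.7 = 13.4; 35.1 - 19.8 = 15.3). It could be far less or more.

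Neither double-blind arm is favoured. The issue matters most for the entire-study percentages, where remibrutinib has no concurrent control after Week 24. The placebo column there covers 7 scheduled visits against 10 for remibrutinib, but that imbalance comes from follow-up length and affects every worst-value laboratory table. The maximum-change table is double-blind only, so it does not affect the long-term groups. Efficacy is untouched. This is a minor, descriptive safety point.

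**What to change.** In SAP 2.7.3, for triglycerides, present the CTCAE newly-occurring/worsening table, the shift tables and the double-blind maximum-change table on fasting samples: Baseline and Weeks 2, 12 and 52.

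- Select on the visit as recorded, not as remapped. SAP 2.1.1.5 remaps early-discontinuation visits to scheduled ones, and its own example uses such a visit as Week 12, so a filter on analysis visit could keep samples with no fasting instruction.
- Exclude from these rows baselines that fall back to screening.
- State how the study-discontinuation visit is treated. It shares the Week 52 column that carries the fasting footnote, but the footnote text names only Week 52.

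Keep the all-visit version beside these rows, labelled as including samples taken without a fasting instruction. Restricting the tables to fasting visits alone would drop any high-grade value seen at the other visits or at unscheduled ones.

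The cost is SAP wording, a visit filter and one extra set of rows for one parameter. The fasting rows rest on only two post-baseline values per participant in the double-blind period.
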